## POL:

Three different types of data will be collected from individuals participating in the POL training program.

Program records, training attendance logs, and observation checklists will be used to record the number and basic sociodemographic profile of POLs recruited, attendance to training sessions, and fidelity of each training session delivered relative to the training curriculum. These records will be primarily kept on paper and scanned or input into a password protected computer database and the team's password protected and encrypted Drexel One-Drive cloud account as needed.

Pre- and post-training questionnaires and weekly practice logs. POLs will complete questionnaires before and after each training session to assess pre/post short-term changes in SAVAME-related knowledge, attitudes, counseling skills, self-efficacy and behavioral intentions to influence and support others, as well as their individual resilience. These questionnaires will cover knowledge, attitudes, self-efficacy, resilience, and behavioral intentions to practice the skills covered during each session. These questionnaires will be completed using the Qualtrics Offline App on project's iPads. While in the initial training phase (first 10 sessions), POLs will also be required to complete weekly paper-and- pencil practice logs detailing their practice of the skills covered during previous training sessions.

For quantitative data, data collected through program logs, observation checklists, pre/post training questionnaires, activity logs and surveys will be entered into datasets (or downloaded from iPads/Qualtrics platform in the case of Qualtrics-based questionnaires or surveys). Process (reach, adoption, implementation) data will be analyzed using descriptive statistics (e.g. means, standard deviations, percents, frequencies, etc.). Given the small sample size (N=10), changes in POL outcomes (e.g. knowledge, behavioral intentions, etc.) will be determined using non-parametric tests for paired data: McNemar's test for binary outcomes and Wilcoxon's Signed Ranks Test for ordinal or interval variables. Analysis will be performed using IBM® SPSS® 22.0 and Stata 14.

The training and experience in the field as a POL is potentially transformative for POLs. At the end of the first month after the completion we will conduct semi-structured qualitative interviews with POLs. After the end of the first-year intervention leaders will be invited to participate in a second-year intervention, an exit interview will be conducted for those that do not wish to continue. For those that accept, the interview will be conducted at the end of the second-year intervention. These interviews will be conducted by trained project staff at TPAC offices. Questions will focus on the self-reported impact the training and application of CRISOL program had on POLs, including their assessment of the level, relevance, and quality of knowledge and skills acquired; impact on self-confidence, resilience, social capital, their role in

the community, and future professional and personal plans. Interview guides will also cover overall satisfaction with the training, challenges to serving as a POL, barriers and facilitators for their role, suggestions for amendments to the training and ongoing support system, and ideas to maximize the impact of CRISOL on the community. This information will guide future improvements of the intervention.

Qualitative interviews with POLs will be audio recorded and transcribed by project staff or by a HIPAA-compliant transcription service (e.g. Transcribeme, Inc.). When outsourcing the transcription work, our team will make sure the audio files are anonymized before sharing them with the transcription services. Transcriptions of the audio files will be coded and analyzed by researchers using thematic analysis and grounded theory, using NVIVO software. Audio files will be destroyed once the information is transcribed. A codebook with a priori codes and emergent themes will be developed after reading a subsample of transcripts. Codes will be subsequently revised and refined. Coding discrepancies and errors will be reconciled by consensus. Emerging themes and the coding/analysis process will be described in a final report.

NVIVO is a password-protected online software, and no POL identifiers will be used when uploading this information for analysis.

For this second year, data collection will be similar as first year. We are updating the pre/post questionnaire to reflect the COVID-19 training. At the end, of the second-year intervention a qualitative interview will be conducted with those that finish the intervention.

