## 7) Study Endpoints

The primary endpoint of this study is to be able to assess the feasibility, acceptability, and efficacy of a peer-driven intervention to address the factors that contribute to this syndemic, increase access to SAVAME and COVID-19 prevention and treatment services, and reduce the prevalence and impact of the syndemic conditions and COVID-19 on the Latino immigrant community in Philadelphia.

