After 1 month of the implementation period (Community experience phase), the research team will conduct a semi-structured interview to gather opinions and overall satisfaction with the training, suggestions for amendments to the training in the future and their experience during the first month of community outreach. At the end of the 8-month implementation period (community experience phase), the research team will conduct semi-structured qualitative interviews with POLs, regardless of their continuation or level of activity. These interviews will

be conducted by trained project staff at TPAC offices. Questions for the exit interview will focus on the self-reported impact the training and application of CRISOL program had on POLs, including their assessment of the level, relevance, and quality of knowledge and skills acquired; impact on self-confidence, resilience, social capital, their role in the community, and future professional and personal plans. Interview guides will also cover challenges to serving as a POL, barriers and facilitators for their role, suggestions for ongoing support system, and ideas to maximize the impact of CRISOL on the community. This information will guide future improvements of the intervention.

POLs will document their activity in the community on the "POL Activity Log Survey" using iPads furnished with an offline Qualtrics® survey. POLs will log every interaction with community contacts and indicate the date, time, and place of the contact. POLs will also document their response to the issues discussed with the community contact which may include modeling of positive social norms, delivery of risk/harm reduction counseling, communication of health messages, linkage to resources, and navigation services to reduce SAVAME risk and impact. Collectively, we expect POLs will reach and register approximately 720 community contacts.

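### Under section 10 of the protocol, a POL who stops during year 2 gets no exit interview; this conflicts with section 8 and tilts end-of-programme evidence toward completers

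*Protocol*

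**What the plan says.** The protocol describes the POL interviews in two places, and both are current text.

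Section 8 (Procedures or Methods Involved, POLs) plans two interviews around the 8-month outreach period of year 1. The early one is timed as follows: "After 1 month of the implementation period (Community experience phase), the research team will conduct a semi-structured interview". It covers views of the training and the early outreach experience. At the end of the 8 months the team is to hold "semi-structured qualitative interviews with POLs, regardless of their continuation or level of activity".

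Section 10 (Data Management, POL) keeps the early interview: "At the end of the first month after the completion we will conduct semi-structured qualitative interviews with POLs". It then splits the later one by whether the POL goes on to year 2. After year 1, "an exit interview will be conducted for those that do not wish to continue". For the others it is postponed: "For those that accept, the interview will be conducted at the end of the second-year intervention". The closing paragraph on year 2 says who is eligible then: "a qualitative interview will be conducted with those that finish the intervention".

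The year-2 timeline in section 6 lists exit interviews and no other POL interview. Section 7 places this evidence within the primary endpoint, which is to "assess the feasibility, acceptability, and efficacy of a peer-driven intervention".

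**The concern.** According to section 10, the exit interview is meant to learn how satisfied POLs were, what made the role hard or easy, and what should change in training and support. Those who stop part-way are best placed to say why POLs stop. An eligibility rule that depends on finishing removes them from the evidence on that very question.

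The deferral adds a second exposure. For a POL who continues, the year-1 exit interview is not held at the end of year 1; it becomes conditional on completing year 2, which section 8 says has nine months of outreach. Section 2 adds that the initial exit instrument was written for a one-year intervention on another topic and that a COVID-19 instrument is now being submitted. Even finishers may therefore give their year-1 account late and to a differently focused set of questions.

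At stake is the feasibility and acceptability evidence that Aim 3 intends for a future grant application.

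**Working it through.** The plan gives no figure to reproduce here. The check sets the two sections side by side and then sizes the exposure with simple proportions.

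**Step 1. Who gets an end-of-period or exit interview?**

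| POL | Section 8 | Section 10 |
|---|---|---|
| Year-1 POL who does not go on to year 2 | Yes, at the end of the 8 months | Yes, after year 1 |
| Year-1 POL who continues and finishes year 2 | Yes, at the end of the 8 months | Yes, but only at the end of year 2 |
| Year-1 POL who continues and stops during year 2 | Yes for year 1; year 2 not addressed | None |
| New year-2 leader who finishes | Not addressed | Yes |
| New year-2 leader who stops | Not addressed | None |

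The sections disagree in rows 2 and 3 about a year-1 exit interview for continuing POLs. In rows 3 and 5 neither section gives a year-2 leaver an exit interview about year 2.

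**Step 2. Inputs.**
- POLs recruited in year 1: 9 (section 20; section 23 gives a target of 10).
- Expected to continue: at least 8 (section 20; section 23 aims to retain 8).
- New year-2 leaders: planned (sections 5 and 8), number not stated.
- POL dropout during year 2: not given. Assumption for scale: 1 to 3 of 8.

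**Step 3. Share of year-1 POLs whose exit interview depends on finishing year 2, if section 10 governs.**

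8 / 9 = 88.9%, about 89%.

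**Step 4. Share of continuing POLs with no exit interview, if section 10 governs.** Share = leavers / 8.
- 1 leaver: 1/8 = 12.5%
- 2 leavers: 2/8 = 25%
- 3 leavers: 3/8 = 37.5%

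With no leavers the share is zero. New leaders are in neither numerator nor denominator, so these are shares of continuing POLs, not of everyone who starts year 2.

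**Step 5. If section 8 governs year 1 instead.** Continuing POLs are interviewed at the end of the 8 months, so no year-1 exit interview is lost. The year-2 gap stays the same, because section 8's inclusive rule is written for the 8-month period only.

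**The case against.** The case on the other side limits the point in several ways.

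- **A reader might infer that year-2 leavers are never interviewed.** The documents do not support that for continuing POLs. Both sections plan an interview one month into outreach, and it covers satisfaction with the training. It cannot, however, explain a departure that comes later. 'Never' could be true only of a new year-2 leader, and only if no such interview is held in year 2. Section 10 says that year-2 data collection resembles year 1, which leaves this open.
- **A reader might infer that acceptability is judged without anyone who quit.** That is too broad. POLs who decline year 2 are interviewed under section 10, and section 8 includes inactive or discontinued year-1 POLs. Attendance records, activity logs, facilitator interviews and community satisfaction surveys do not depend on the exit interview. They would show attrition and falling activity, but not a leaver's reasons.
- **A reader might infer that year-1 data are certainly lost.** That follows only if section 10 overrides section 8, and neither section says which prevails.
- **A reader might try to correct an acceptability percentage for the missing leavers.** No such percentage is planned. The interviews are analysed thematically, so the selection affects which themes are heard, not a reported rate.
- **The interviews are few, and the SAP's co-primary outcomes concern community contacts.** Both statements are true. The SAP outcomes are unaffected, but acceptability still stands in the protocol's primary endpoint.
- **Section 12 stops all data collection when a participant withdraws.** This stands, and any change must respect it.

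What survives all of this is that a mid-year-2 leaver has no exit interview, and that sections 8 and 10 contradict each other for continuing POLs.

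**Conclusion.** The point holds in a limited form. As written, section 10 makes the year-2 exit interview conditional on finishing, and it makes the year-1 exit interview of continuing POLs conditional on the same thing. This conflicts with section 8 and selects the end-of-programme evidence on acceptability and barriers toward completers.

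The size depends on a dropout figure that the documents do not give. About 8 of 9 year-1 exit interviews are exposed if section 10 governs, and 12.5% to 37.5% of continuing POLs would have no exit interview if 1 to 3 of 8 left. Both statements assume that exactly 8 continue and leave out new leaders. The direction of selection is clear from the rule. How far it would change the themes cannot be worked out from the documents.

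**What to change.** 1. Reconcile sections 8 and 10, so that one rule says who has an exit interview and when.
2. In section 10, replace the restriction to finishers with wording such as: *all POLs who started year-2 training, whether or not they carried on and however active they were, interviewed when they stop or at the end, unless they have withdrawn from the research (section 12)*. This separates ending the POL role from withdrawing from the study.
3. State when continuing POLs answer the year-1 exit questions, and with which instrument.
4. Report themes for finishers and leavers separately, with the number approached and interviewed in each group.

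**Cost.** A few more interviews by the same staff; section 2 already allows phone or online data collection. At the $25 that section 14 offers for the year-2 exit interview, 1 to 3 leavers would cost 1 × $25 = $25 to 3 × $25 = $75, plus transcription and coding. Some leavers may decline, so the gap would narrow rather than close.

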#### Community contacts:

As described above, after graduation, POLs will document their activity in the community using iPads furnished with an offline Qualtrics® survey. POLs will log every community contact they complete and indicate the date, time, and place of the contact ("POL Activity Log Survey"). For each community contact, POLs will document their community contacts' responses to the issues identified, which may include modeling of positive social norms, delivery of risk/harm reduction counseling, communication of health messages, linkage to resources, and navigation services to reduce SAVAME risk and impact. POLs will offer the community contact to take a satisfaction survey. The first survey ("Satisfaction Survey") can be self-administered by the community member and is designed to collect data on basic sociodemographic characteristics (e.g. age, gender, sexual orientation, race/ethnicity, etc.) and their satisfaction with the services received from the POL.

Collectively, we expect POLs will reach and register approximately 720 community contacts. These data will serve to establish the level of reach, implementation (feasibility), and maintenance of the intervention in the community and provide important community-level baseline data to describe the population reached by the POLs.

These quantitative data will be analyzed as follows: Parametric (one-way repeated measures ANOVA) or non-parametric tests (Friedman's test, general estimated equations), depending on

the level of measurement and observed distribution of the information. Analysis will be performed using IBM® SPSS® 22.0 and Stata 14.

All surveys offered as part of data collection on the community contact section of this protocol will be collected with and stored in Qualtrics®.

For the second year, we expect to follow same procedures as prior year. Additionally, we will be inviting community members to participate in an additional survey that measures risk behaviors and protective factors for SAVAME and COVID-19, as well as sociodemographic characteristics. After 3 months, those that expressed interest and gave consent will be contacted to complete a follow-up survey. These surveys will be collected and stored using Qualtrics ®.

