#### Community contacts:

Post interaction with POLs, community members will complete a brief anonymous "Satisfaction Survey" based on their interaction with the POL, in addition to basic sociodemographic

characteristics. Community members will be provided with the informed consent script and must agree to participate before beginning the survey. The CRiSOL survey would be self-administered when the POLs and community contacts meet face-to-face, or administered by the POLs when interactions are made via phone or other media. The latter situation will be the case when social distancing measures are in place due to the coronavirus. The survey relies on Qualtrics®.

Note that by closing the survey, the answers of the individual cannot be accessed anymore except by the research team and no names or identifying information is included in the survey. A small incentive (i.e. a tote bag with the logo of the project) will be given to participants for their time when interactions are done face to face. This will not be possible when interactions are not face to face, such as during the coronavirus crisis.

For this second year, the study will be similar. Community members will complete an anonymous brief "satisfaction survey" after giving verbal consent (use of short consent version). Additionally, for this second year we are adding a new survey. POLs will invite community members to participate and collect phone numbers of the ones that agree. The research team will contact the community members that expressed interest, provide with a copy of the verbal consent and provide a link for them to take the survey. This survey will not collect any personal data. 300 community contacts will be invited to complete a follow-up survey 3 months after the completion of the first survey. The personal information needed to contact participants (i.e. phone number and first name) will be stored in a password-protected document.

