#### 20) Resources Available

We recruited 9 POLs and plan to recruit 720 community contacts. These numbers are based on several factors: a) Resources (funds and personnel) and time available to the project; 2) Previous experience conducting research with Latino populations by the study team; 3) Size of the Latino population in Philadelphia; and 4) Discussions with our community partners.

We expect that at least 8 POLs will continue during the second year. Additionally we plan to recruit 720 community contacts, from which 300 will filled the additional surveys.

Our team has the following **people-based resources** available to us to conduct the study:

• [name] (myself): I am an associate professor in the Department of Community Health and Prevention at the Drexel University Dornsife School of Public Health. My academic training, cultural background, and research experience have prepared me well to direct this study. I have a PhD in health psychology and my postdoctoral work focused on HIV prevention and tobacco control research with Latino populations. I am a fully bilingual Latina. During the last 11 years, I have been serving as PI for NIH-funded research aimed at estimating the risk for HIV infection, identifying risk determinants, and examining health care access among Mexican migrants and immigrants. In recognition of the novelty and potential of this work, I received a Presidential Early Career Award for Scientists and Engineers in 2009. I have served as principal investigator and co-investigator for a number of research studies examining

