#### 23) Number of Subjects

This study aims to recruit and train 10 POLs and 720 community contacts. And for the second year, aims to retain 8 POLs and recruit a total 720 community contacts.

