Baseline and demographic characteristics will be summarized overall for all patients and for those with complete follow up. Univariate summary statistics will be provided for continuous variables and frequencies for categorical variables. Paired t-tests and test of proportions, will be used to assess changes in these outcomes from baseline to 3 months.

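### Repeated-measures ANOVA and Friedman's test are assigned to community-contact data that include an anonymous, unlinkable Satisfaction Survey, and GEE is named without POL as the cluster

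*Protocol*

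**What the plan says.** Protocol section 10 (Data Management, Community contacts) describes two year-1 sources: the Activity Log, which the POL completes for each contact with date, time and place, and the Satisfaction Survey, which the contact may complete. It gives the expected volume ("Collectively, we expect POLs will reach and register approximately 720 community contacts") and says the data will serve to establish reach, implementation and maintenance. The analysis sentence follows directly: "These quantitative data will be analyzed as follows: Parametric (one-way repeated measures ANOVA) or non-parametric tests", with the non-parametric options given as "Friedman's test, general estimated equations), depending on" measurement level and distribution.

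On linkage, section 8 (Community contacts) says of the Satisfaction Survey that "no names or identifying information is included in the survey". Section 24 (Confidentiality) describes it as anonymous, with no contact details taken.

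The year-2 text comes after the analysis sentence: "For the second year, we expect to follow same procedures as prior year". It then adds a separate survey with a 3-month follow-up. The SAP gives that survey its own analysis: "Paired t-tests and test of proportions, will be used to assess changes in these outcomes from baseline to 3 months".

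The POL part of section 10 lists activity logs and surveys among the quantitative data and assigns descriptive statistics to reach, adoption and implementation.

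On POL numbers, section 20 says "We recruited 9 POLs and plan to recruit 720 community contacts" and section 23 says "This study aims to recruit and train 10 POLs and 720 community contacts". For year 2, section 23 aims to retain 8 POLs and recruit 720 contacts.

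**The concern.** Repeated-measures ANOVA and Friedman's test compare two or more linked measurements on the same unit. The Satisfaction Survey yields unlinked records. Even if a person meets a POL twice and answers twice, the two answers cannot be joined. For this survey the sentence therefore names tests that do not apply, which goes beyond leaving out detail.

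The dependence that does exist is of another kind. Contacts come from each POL's own network and rate that POL, so answers within a POL may be correlated. GEE could handle this, but it appears only as a non-parametric fallback, with no cluster unit and no allowance for having so few clusters.

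Acceptability and feasibility are part of the primary endpoint (section 7), and the pilot is meant to inform a later effectiveness trial (section 3). Treating several hundred satisfaction records as independent would overstate the precision of one of its main results.

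**Working it through.** **1. Reproduce the contact count.** Section 6 commits each POL to at least 5 contacts per two weeks. Section 8 gives 16 biweekly meetings, taken here as 16 two-week periods.
- Year 1: 9 POLs × 5 × 16 = 720, the stated figure. With the target of 10 POLs: 10 × 5 × 16 = 800, which does not match.
- Year 2 (section 8: at least 10 contacts per month for 9 months): 8 × 10 × 9 = 720, the stated figure.

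**2. Contacts per POL.** 720/9 = 80; 720/10 = 72; 720/8 = 90.

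**3. Can the named tests be applied?** With n units and k linked measurements, the within-unit degrees of freedom are (k − 1) and (n − 1)(k − 1).

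| Data | n | k | df |
|---|---|---|---|
| Satisfaction Survey, unlinked | 720 | 1 | 0 and 0 |
| Activity Log totals, POL by two-week period | 9 | 16 | 15 and 120 |
| Year-2 survey, before dropout | 300 | 2 | 1 and 299 |

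The first row cannot be analysed by repeated-measures ANOVA, and Friedman's test also needs k of at least 2. The second row works if log entries carry a POL code. The third works if the waves are linked, but the SAP governs that survey.

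**4. Effect of clustering on a satisfaction proportion.** The documents give no ICC and no expected satisfaction rate. Both are assumptions here: ICC 0.01 to 0.05, and 80% satisfied. All 720 contacts are taken to respond, equally spread over POLs.
- Design effect = 1 + (m − 1) × ICC. With m = 80: 1.79 at 0.01, 2.58 at 0.02, 4.95 at 0.05.
- Effective sample size = 720 / design effect: about 402, 279 and 145.
- Standard error under independence = √(0.8 × 0.2 / 720) = 1.49 points. Half-width = 1.96 × 1.49 = 2.9 points.
- Clustered, ICC 0.02: 2.92 × √2.58 = 4.7 points.
- Clustered, ICC 0.05: 2.92 × √4.95 = 6.5 points.
- With t on 9 − 1 = 8 degrees of freedom (2.306 in place of 1.96): 1.491 × 2.306 × √2.58 = 5.5 points, and 1.491 × 2.306 × √4.95 = 7.6 points.

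**5. Sensitivity to the number of POLs** (multiplier 1.96).
- 10 POLs (m = 72): design effects 2.42 and 4.55; half-widths 4.5 and 6.2 points.
- 8 POLs (m = 90): design effects 2.78 and 5.45; half-widths 4.9 and 6.8 points.

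**6. The two parts of section 10 side by side.** The POL part makes reach and implementation data descriptive and counts activity logs among its sources. The Community contacts part says its data establish reach and implementation, then assigns inferential tests. Neither says which governs.

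**The case against.** A reader might infer that the stated analysis cannot be run at all and that clustering is ignored. The documents do not support that, for four reasons.

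- GEE is in the same sentence and is a standard method for clustered data. The dependence is left unspecified rather than ignored.
- The descriptive analysis in the POL part of section 10 gives a workable route for reach and implementation, with no test involved.
- The Activity Log is dated and maintenance is a question over time. POL-by-period totals could support a repeated-measures test if entries can be attributed to POLs.
- Absence of linkage is firm only for the Satisfaction Survey. Section 13 mentions unique identifiers for community contacts without saying for which data. Section 5 requires a log entry at every interaction, so one person may appear more than once.

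All four stand, and they limit the point. They do not remove it. No source is matched to a method, the two within-unit tests do not fit the anonymous survey, GEE lacks a cluster unit, and the descriptive plan and the inferential sentence disagree.

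It is also fair to say that the magnitude is illustrative. The plan states no satisfaction threshold, hypothesis or interval. The SAP does not close the gap, because it lists only baseline and 3-month outcomes.

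**Conclusion.** The point holds in limited form. Repeated-measures ANOVA and Friedman's test have no repeated factor in the Satisfaction Survey, GEE is named without POL as the cluster, and the two parts of section 10 conflict on reach and implementation data.

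If satisfaction records were analysed as independent, the half-width of about 2.9 points would be too narrow by a factor of 1.6 (√2.58) at ICC 0.02 and 2.2 (√4.95) at ICC 0.05, before any allowance for few clusters. This rests on the assumed ICCs, the assumed 80% satisfaction, full response and equal cluster sizes. Fewer respondents would widen every interval. The non-applicability of the two tests to the anonymous survey rests on none of these assumptions.

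This should be corrected. It concerns the acceptability and process results, and the remedy is cheap.

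**What to change.** Replace the analysis sentence in section 10 (Community contacts) and reconcile it with the POL part of the same section. For each data source, state the outcome, unit, time points and linkage.

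- **Satisfaction and contact-level log data.** Record a non-identifying POL code on every survey and log record; the documents do not say that such a field exists, and the clustered analysis depends on it. Report proportions or means with 95% confidence intervals clustered by POL, using the GEE already named or a mixed model, with a small-sample correction and a t reference on the number of POLs minus 1.
- **Reach and activity over time.** Keep reach counts descriptive. Limit repeated-measures ANOVA and Friedman's test to POL-level activity per two-week period.
- **Year-2 baseline and 3-month survey.** Analyse it under the SAP, but not with the SAP's tests unchanged. State how the two waves are linked, specify a paired test for proportions (such as McNemar's, which the Protocol already names for POL outcomes), and account for POL clustering, which the SAP does not mention.

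The cost is protocol and SAP wording, one added code field, slightly more analysis, and wider, less favourable intervals.
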